4.1 OVERVIEW OF STUDY DESIGN/INTERVENTION

4.2 Design

This is a single-arm Phase II trial testing the efficacy of concurrent cisplatin and radiation in breast cancer patients with measurable metastatic or locally recurrent tumor, based on HRR status as determined by the MSK-HRR assay. Prior to study enrollment, all patients will require assessment by the radiation oncologist and medical oncologist. Patients will receive a baseline PET-CT +/- MR for evaluation of the tumor to be irradiated and to assess extent of disease systemically. If unavailable within the time specifications of the study, the PET-CT +/- MR will be performed after study registration. Biopsy of the tumor to be irradiated will be performed. Fresh tissue specimens will be sent to the laboratory of [name] for performance of the MSK-HRR Assay. Results from the functional assay will be utilized towards the primary endpoint. Additional unutilized tissue will be sent to the Immune Monitoring Facility Laboratories for TIL analyses to be conducted by [name]. Bloodwork will be sent to the lab of [name] for ctDNA analyses. After the biopsy, patients will undergo simulation for palliative radiation to the tumor site. Following simulation, patient will initiate a 25 mg/m² infusion of cisplatin once a week \pm 3 days. The starting dose will depend on baseline laboratory results within 28 days prior to registration. Following 1-2 weeks of cisplatin, RT will be initiated. Weekly cisplatin (\pm 3 days) will be continued and delivered concurrently with RT. After the completion of RT, weekly cisplatin (\pm 3 days) will be continued until disease progression or until assessment of treatment response at Week 12 post RT (+/- 2 weeks), based on MD discretion. Patients whose HRR status is found to be inevaluable by the MSK assay will not be included in the study and will be replaced by eligible patients.

At Week 12 (12 \pm 2 weeks after RT; with strong recommendation at 12 weeks), repeat imaging with the same imaging methods used for baseline assessment will be performed. Treatment response will be

determined by either PRC or RECIST 1.1.

We estimate accrual will occur at the rate of 15 patients per year. It will take 3.5 years to accrue the total of 54 patients. Patients will be followed up to 24 weeks after completion of RT to determine all study endpoints. Clinical follow-up will continue until death.

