13.0 CRITERIA FOR REMOVAL FROM STUDY

Participants will be removed from the protocol for any of the following reasons:

- Development of disease progression that warrants a change in the radiation or chemotherapy treatment plan or an alternative therapy.
- Any grade 4 non-hematologic toxicity, except in cases where the treating physician believes the patient is deriving benefit from remaining on the study.
- Chemotherapy treatment delay of 3 consecutive weeks for any reason
Note: Disruption to the cisplatin treatment schedule for 3 weeks due to unforeseen circumstances, holidays or the patient being on vacation is permitted and will be reviewed on a case-by-case basis.
- For safety reasons, the investigator considers it to be in the best interest of the participant that they be withdrawn
- The patient wishes to withdraw from the study
- HRR status is unable to be obtained from the core biopsy taken at the beginning of the study.

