However, we will plan to accrue a total of **62** patients in order to allow for early dropout due to disease progression/death prior to response evaluation, or inability to obtain HRR status from the core biopsy. For the primary analysis, all patients for whom HRR status can be ascertained will be included in the denominator. Patients who progress or die prior to the response evaluation at 12 +/- 2 weeks post-RT will be included as failures. This includes patients with disease progression outside of the irradiated tumor. Patients for whom HRR status cannot be ascertained or who left the study for nondisease related reasons will be replaced.

A secondary analysis of interest is to evaluate the CR rate among the subset of patients who are able to complete the planned study treatment and have a scan at the 12 +/- 2 week post-RT time point. Radiographic complete response (CR) of the irradiated tumor will be counted as a positive response to treatment. Radiographic response less than a CR, progression of the irradiated tumor or appearance of a new lesion within the radiated field will be categorized as a failure to respond to treatment. All other sites of metastatic disease that is outside of the irradiated field will be monitored and counted toward disease progression.

Based on prior experience with the HRR assay, we estimate that approximately 10% of patients will either 1) not have a definitive HRR status, or 2) will not complete the planned study treatment or 3) not have a response assessment at 12-14 week time point. To ensure we have 80% power for both the primary and secondary analyses we have added 8 patients to the sample size for a total of 62. The accrual number has been adjusted to 54 patients.

We expect to accrue 1 to 2 patients per month, or approximately 18 patients per year. Thus, accrual for the trial will be completed in 3.5 years. Based on previous data on the tolerability of cisplatin and radiation extrapolated from head and neck and gynecologic malignancies, we do not anticipate toxicities associated with the study treatment and as such, we have not incorporated an early stopping rule.

Secondary endpoints include overall response rates (CR+PR+stable disease), time to progression and CTCAE v4.0 toxicities. These endpoints will be compared by HRR status using the log-rank test for time-to-event endpoints and Fisher's exact test for binary endpoints.

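### Section 14.0 still credits 80% power for two analyses to 8 extra patients, but accrual is now 54, and the plan does not say whether 54 means enrolled or evaluable

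*Combined protocol and SAP*

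**What the plan says.** Section 14.0 tabulates power for n=54 (CR 65% versus 30%, one-sided 5%): 85%, 83% and 80% when 40%, 35% and 30% of patients are HRR-deficient. It then plans to accrue 62, "in order to allow for early dropout due to disease progression/death prior to response evaluation" or because the biopsy yields no HRR status.

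On losses it says "we estimate that approximately 10% of patients will either 1) not have a definitive HRR status", or will not complete treatment, or will have no response assessment. The purpose of the extra patients is given as "To ensure we have 80% power for both the primary and secondary analyses". The text continues: "we have added 8 patients to the sample size for a total of 62. The accrual number has been adjusted to 54 patients". No reason, revised loss allowance or revised power follows.

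Section 1.0 gives 54 as the target accrual. Section 4.2 says "It will take 3.5 years to accrue the total of 54 patients".

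For the primary analysis, Section 14.0 keeps every patient with a known HRR status and counts progression or death before the scan as failure. It adds: "Patients for whom HRR status cannot be ascertained or who left the study for nondisease related reasons will be replaced". The secondary analysis of CR is restricted to patients who complete treatment and have the 12-week scan (the completer analysis below).

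On patients with no HRR result, Section 4.2 says they "will not be included in the study and will be replaced by eligible patients". Section 13.0 lists as a reason for removal that "HRR status is unable to be obtained from the core biopsy taken at the beginning of the study". Section 5.3 leaves them out of the primary analysis but counts them for the secondary and exploratory objectives.

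**The concern.** The allowance for loss was the stated reason for 80% power in two analyses. The allowance has gone and the power statement has stayed. The remaining figure, 54, is the number the table needs after losses. At 30% HRR-deficiency it has no slack: by the formula that reproduces the table, 54 is the smallest number reaching 80%.

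The word accrual suggests that 54 is the number enrolled. The n=54 table and the replacement rule suggest that it is the number evaluable. As written, staff cannot tell when enrolment closes, and a reader cannot tell how many patients each analysis is meant to contain or what power it has.

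**Working it through.** **Inputs.** All from Section 14.0: CR 30% (HRR-proficient) and 65% (HRR-deficient), one-sided 5%, HRR-deficient share f = 40/35/30%, table n = 54, earlier accrual 62, expected loss about 10%. The plan names no power formula.

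**1. Reproducing the table.** With n2 = fN deficient and n1 = (1−f)N proficient patients, the unpooled normal approximation is

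SE = √[p1(1−p1)/n1 + p2(1−p2)/n2], power = Φ[(p2−p1)/SE − 1.645].

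At N = 54, f = 40%: n1 = 32.4, n2 = 21.6, SE = √(0.21/32.4 + 0.2275/21.6) = 0.1304, and power = Φ(0.35/0.1304 − 1.645) = 85.0%. The other rows give 83.2% and 80.4%. All three match the table. The pooled-variance version gives 82.8/81.1/78.4% and does not match, so the unpooled form is used below.

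**2. Numbers after 10% loss.** 62 × 0.9 = 55.8, about 56. 54 × 0.9 = 48.6, about 49. To keep 54 after loss: 54/0.9 = 60.

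**3. Primary analysis.** Early progression and death stay in the denominator, so only a missing HRR status or a non-disease withdrawal can shrink this set, and both are replaced.
- Replacements additional to 54: 54 analysed, 85/83/80%. Enrolment is between 54 (no one needs replacing) and about 60 (the whole 10% does).
- Replacements within 54: between 54 and about 49 analysed. The floor is reached only if the whole 10% is missing HRR status or non-disease withdrawal. Power at 49 is 81.9/79.9/76.9%, or 82/80/77% rounded; the 35% row is just under 80%.

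**4. Completer analysis.** Early progression or death removes a patient from this set and is not replaced, so completers can fall to about 49 under either reading of 54. Power then depends on the CR rates among completers, which the plan does not give.
- (a) 65% versus 30% carries over: 82/80/77% at 49. With 62 enrolled and about 56 completers it would be 86/84/82%.
- (b) All of the 10% loss is early progression or death, already counted as failure in the primary set and equal in both HRR groups. Removing those failures raises the rates to 0.65/0.9 = 72.2% and 0.30/0.9 = 33.3%. At N = 49, f = 40%, SE = 0.1334 and power = Φ(0.389/0.1334 − 1.645) = 90%. The three rows are 90/89/86%.

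| Set | N | 40% | 35% | 30% |
|---|---|---|---|---|
| Table, primary if replacements are additional | 54 | 85% | 83% | 80% |
| Primary floor if replacements fall within 54 | 49 | 82% | 80% | 77% |
| Completers, 65% vs 30% | 49 | 82% | 80% | 77% |
| Completers, 72% vs 33% | 49 | 90% | 89% | 86% |

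**5. Timeline.** Section 14.0 gives 18 patients per year and 3.5 years. That fits 62 (62/18 = 3.4 years) better than 54 (54/18 = 3.0). Section 4.2 gives 15 per year, which fits 54 (54/15 = 3.6). This agrees with Section 14.0 having been only partly updated.

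**The case against.** The strongest reply is that 54 is plainly the operative number, since Sections 1.0, 4.2 and 14.0 all give it, so what remains is leftover wording with little effect. No entry in the power table is wrong. Section 4.2 excludes and replaces patients without an HRR status before giving the total of 54, so the natural reading places replacements outside the 54 and leaves primary power as tabulated. This stands, and it limits the size of the point.

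A reader might infer that the completer analysis loses its 80% power at 30% HRR-deficiency. The documents do not establish that. The 77% figure needs 65% versus 30% to hold among completers, whereas the plan's own rules remove primary-analysis failures from that set, which tends to raise CR rates. Case (b) stays above 80% in every row. It is an assumption too: some patients who do not complete treatment may have responded, and loss may differ by HRR status.

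A reader might also infer that four sections conflict over patients without an HRR status. Removal, non-inclusion, replacement and exclusion from the primary analysis are compatible. The real conflict is between Section 4.2, which leaves these patients out of the study, and Section 5.3, which counts them for other objectives.

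Finally, the formula is inferred. Pooled variance lowers power at 54 by about 2 points, close to the 3-point drop from 54 to 49, so small differences around 80% should not be over-read.

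The reply does not remove the core defect: the current text guarantees 80% power by means of patients who are no longer planned, and does not define 54.

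**Conclusion.** Wrong as written; minor to should-fix. The statement that 8 added patients secure 80% power for both analyses has lost its basis, and the plan does not say whether 54 is enrolled or evaluable.

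The consequence is modest. Primary power most likely remains as tabulated, with a worst case 3 to 4 points lower. At the 40% planning value every scenario examined exceeds 80%. Completer power cannot be fixed from the documents; the two cases worked give a range of 82–90%, 80–89% and 77–86% across the three rows.

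These figures rest on the unpooled formula, the plan's 10% loss, and loss unrelated to HRR status. They do not show that the trial is underpowered at its planning assumptions.

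**What to change.** In Section 14.0:
- Delete the 62 and the added-8 wording.
- State whether 54 is enrolled or evaluable. If evaluable, keep the table for the primary analysis, give expected enrolment (up to about 60 at 10% loss), and align the accrual wording in Sections 1.0 and 4.2. If enrolled, give primary power as a range from 54 analysed down to the 49-patient floor, and say in Sections 4.2 and 14.0 that replacements fall within 54.
- Replace the blanket 80% claim for the completer analysis with power at the expected number of completers, under stated completer CR rates and shown as a range. Neither 82/80/77% nor 90/89/86% should be entered alone.
- Name the power formula.

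Reconcile Sections 4.2 and 5.3 on whether patients without an HRR status belong to the study and count towards 54. As minor clean-up, use one accrual rate (15 or 18 per year).

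The cost is text only. The downside is either a stated enrolment up to about 6 higher (60 − 54) or a slightly lower worst-case power.

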3.3 Rationale for Concurrent Cisplatin and RT

Biologically, cisplatin is a known radiosensitizer, with both additive and synergistic potentiation of radiation. Platinum potentiates radiation-induced cell injury through a number of putative mechanisms. These agents act via formation of DNA cross links resulting in DNA double-strand breaks. When cisplatin is integrated into DNA adjacent to a radiation-induced single cell strand break, it can make the break more difficult to repair and thus lead to cell death [15,16]. In addition, cisplatin increases cellular platinum uptake [16], and enhance formation of toxic platinum intermediates [17]. The potentiation of radiation-induced cell injury appears under both oxic and hypoxic conditions [18].

Preclinical studies have shown that the combination of cisplatin and RT delivers the maximum ex-vitro stress response needed to stimulate HRR repair, compared to cisplatin or RT when delivered individually. Mouse embryo fibroblast cells with mutated DNA repair pathways were measured for responses after cisplatin, radiation and combination treatments. The combination treatment showed that inhibition of the HRR pathway resulted in super additive effects, compared to cisplatin or RT alone [19].

Concurrent cisplatin and radiation treatment is standard of care in the definitive treatment of advanced head and neck as well as cervical cancer [20-30]. A large meta-analysis has established the survival benefit of concurrent chemoradiation versus RT alone for head and neck cancer [27]. The efficacy and safety profile of concurrent cisplatin and RT in cervical cancer has also been well established in randomized trials [20-24]. The toxicities of concurrent cisplatin and RT are specific to the irradiated site but are generally tolerable. Adverse events among cervical cancer patients who received both cisplatin and RT included 12% grade 3 leukopenia, 1.1% thrombocytopenia, 5.6% other hematologic toxicities and 4.5% grade 3 gastrointestinal toxicities. Grade 2 toxicities included 14.7% leukopenia, 2.3% thrombocytopenia, 15.3% other hematologic toxicities and 15.9% gastrointestinal toxicities. No treatment-related deaths were reported in these trials.

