6.3 Subject Exclusion Criteria

- Unmeasurable target tumor site by RECIST 1.1 or PRC (ex: lesions <2 cm on CT or MR scan, leptomeningeal disease, ascites, pleural/pericardial effusion, lymphangitis, non-FDG-avid skin lesions)
- Brain metastases requiring focal or whole brain radiation will be excluded, as these lesions cannot be biopsied and can have life expectancies <6 months.
- Inability to obtain a biopsy of the tumor as deemed by the study Interventional Radiologist
- Prior chemotherapy completed <7 days prior to planned study entry
- Prior RT is allowed and must have been completed more than 7 days before planned study entry.

Note: For re-irradiation cases, standard departmental guidelines should be followed so as to not exceed normal tissue

- Life expectancy less than 6 months
- Intercurrent illness or other major medical condition or comorbid condition that might affect study participation (uncontrolled renal, pulmonary or hepatic dysfunction or infection)
- Renal dysfunction for which cisplatin dose would be considered unsafe.
- Women on study must be neither pregnant nor nursing nor expected to become pregnant during therapy. For premenopausal women, negative pregnancy test within 14 days of RT is required.
- Concurrent active malignancy other than non-melanomatous skin cancer or carcinoma in-situ of the cervix, unless treatment for the previous cancer was completed >2 years prior to study entry and patient has remained disease-free.

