Myelosuppression occurs in 25-30% of subjects treated with cisplatin. The nadirs in circulating platelets and leukocytes occur between days 18 and 23, with most subjects recovering by day 39. Leukopenia and thrombocytopenia are more pronounced at higher doses (>50 mg/m²) than will be administered in this study. Anemia (a decrease in hemoglobin of 2gm.100 ml) occurs at approximately the same frequency and with the same timing as leukopenia and thrombocytopenia.

Neurotoxicity

Cisplatin neurotoxicity is characterized by peripheral neuropathies, which are sensory in nature but can also include motor difficulties such as reduced deep-tendon reflexes and leg weakness. The symptoms usually occur after prolonged therapy (4-7 months). Cisplatin therapy should be discontinued when serious neuropathy develops (defined in Section 4.2.1). The neuropathy, however, may progress further even after discontinuation of treatment.

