11.4 Toxicities of Radiation

Toxicities may occur from radiation treatment. The type and risk of toxicity will depend on the presence of normal tissue structures in close proximity to the target. These normal tissue doses will be constrained by the treatment plan to deliver doses no more than those recommended in our departmental guidelines:

(<http://teamshare/dept/medphys/ebtp/Public%20Documents/Forms/Public%20View.aspx>)

The estimated risk of each type of toxicity is noted below, and include:

1. Skin (erythema, dry or moist desquamation, patchy ulceration) - 40-50%
2. Non-debilitating fatigue- 50%

3. Brachial plexopathy- 5-7%
4. Bowel (bowel perforation, obstruction or hemorrhage) - 2-5%
5. Peripheral nerve (neuropathy or severe neuropathic pain unresponsive to medications)-2-5%
6. Bladder (hemorrhagic cystitis, chronic cystitis manifesting in frequency and urgency) - 2-5%
7. Rectum (injury including ulceration or perforation)-2-5%
8. Osteonecrosis or bone fracture- 5-10%

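### Section 14.0 waives an early stopping rule because toxicities are not anticipated; the protocol's own figures contradict that reason, and no aggregate toxicity trigger is stated

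*Combined protocol and SAP*

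**What the plan says.** Section 14.0 (Biostatistics) states: "we do not anticipate toxicities associated with the study treatment and as such, we have not incorporated an early stopping rule". The basis offered is the "tolerability of cisplatin and radiation extrapolated from head and neck and gynecologic malignancies".

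Other sections give toxicity figures:

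- Section 3.3 (Rationale for Concurrent Cisplatin and RT) reports that adverse events with the combination in cervical cancer "included 12% grade 3 leukopenia, 1.1% thrombocytopenia, 5.6% other hematologic toxicities and 4.5% grade 3 gastrointestinal toxicities". It adds: "The toxicities of concurrent cisplatin and RT are specific to the irradiated site but are generally tolerable".
- Section 11.2: "Myelosuppression occurs in 25-30% of subjects treated with cisplatin". No grade is given.
- Section 11.4 gives percentage risks that depend on the structures near the target. One entry is "Osteonecrosis or bone fracture- 5-10" per cent; others are brachial plexopathy at 5-7% and skin toxicity at 40-50%.
- Section 11.1 defines a severe toxicity as a grade 3 event attributed to radiation or chemotherapy and seen within 2 months of finishing radiation. No section links that definition to a count or a rate.

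Section 2.0 makes toxicity a secondary objective. The only toxicity analysis in Section 14.0 is a comparison by HRR status using Fisher's exact test.

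**The concern.** The waiver rests on a single premise, and the rest of the protocol does not share it. The document lists expected toxicities with rates, sets rules for holding cisplatin when they occur, and makes them a study objective.

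The extrapolation is also weak on the protocol's own terms. Section 3.3 says toxicity is specific to the irradiated site, yet the tolerability data come from other sites. The population differs too. Section 6.2 admits ECOG performance status 2 and any prior chemotherapy, including platinum. Section 6.3 says "Prior RT is allowed and must have been completed more than 7 days before planned study entry", and Section 4.3.2 provides for overlap with earlier fields.

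What is at stake is patient safety across the cohort. If severe toxicity were more frequent than expected, nothing in the plan says at what count anyone must look. The end-of-study comparison would not reveal it either: if both HRR groups had the same high rate, Fisher's test would show no difference and say nothing about whether the regimen is tolerable.

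**Working it through.** **The plan's own figure.** Section 14.0 contains no safety calculation to reproduce. Its only design figures are the powers of 85%, 83% and 80% for complete response. An unpooled one-sided z-test gives 85.0%, 83.2% and 80.4%, so they reproduce, but they have no bearing on this point.

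**Step 1: does the premise fit the stated rates?** Inputs are the four Section 3.3 rates (12%, 1.1%, 5.6%, 4.5%) and the 54 patients to which Section 14.0 adjusts accrual.

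- Leukopenia alone: 54 × 0.12 = 6.5 patients expected. P(at least one) = 1 − 0.88^54 = 99.9%.
- All four categories, if independent: 1 − (0.88 × 0.989 × 0.944 × 0.955) = 21.5%, or 11.6 of 54 patients.
- All four, if mutually exclusive: 12 + 1.1 + 5.6 + 4.5 = 23.2%, or 12.5 of 54 patients.

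The documents do not say how the categories overlap. With complete overlap the combined rate would fall to 12%. A grade is printed for only two of the four. So 21.5-23.2% is an assumption-based upper range, not a stated rate.

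**Step 2: what the plan would do about an excess.** No section ties an aggregate count to a review. The probability of a pre-specified flag is therefore 0 at every true rate, and planned enrolment stays at 54.

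**Step 3: what a trigger could do (illustration only).** The protocol states no acceptable rate, so ceilings p0 of 15% and 20% are assumed. Looks are at 10, 20, 30 and 40 patients. The boundary is the smallest count for which the posterior Pr(rate > p0) is at least 0.95 under a Beta(p0, 1 − p0) prior. This gives 4/7/9/11 events for 15% and 5/8/11/13 for 20%. Pause probabilities are the exact binomial chance of first reaching the boundary, summed over looks. For the 15% ceiling at a true 15%, that is 5.0 + 1.0 + 1.2 + 1.0 = 8.2%.

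| True rate | 15% ceiling (4/7/9/11) | 20% ceiling (5/8/11/13) |
|---|---|---|
| 15% | 8% | 2% |
| 20% | 25% | 8% |
| 21.5% | 33% | 12% |
| 23.2% | 42% | 17% |
| 30% | 76% | 49% |
| 35% | 91% | 73% |
| 40% | 97% | 89% |

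**Step 4: lag.** A patient's severe-toxicity status is complete after 1-2 weeks of cisplatin, 3-5 weeks of radiation (longer with a boost) and 2 months (8.7 weeks), which is 12.7 to 15.7 weeks. Section 4.2 expects 15 patients a year and Section 14.0 expects 18. So between 15 × 12.7/52 = 3.7 and 18 × 15.7/52 = 5.4 more patients enrol before a look is complete. At a true 35% under the 15% ceiling, mean enrolment is 21.6 without lag and about 25-26 with 4-5 extra patients. Expected events are then about 9 (0.35 × 25.3 = 8.8; 0.35 × 26.2 = 9.2), against 0.35 × 54 = 18.9 at full accrual.

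**The case against.** The strongest reply is that the sentence is loosely worded and means no unexpected or unacceptable toxicity. Section 3.3 calls the combination generally tolerable and reports no treatment-related deaths in the cited cervical trials. It also describes weekly doses of 30-50 mg/m² as well tolerated, and this trial plans 25 mg/m². Section 11.2 says leukopenia and thrombocytopenia are more pronounced above 50 mg/m². This stands as a reason for a modest rule, or for a reasoned waiver. It does not rescue a waiver whose only stated reason is that toxicity is not anticipated.

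The second reply is that safeguards exist, and they do:

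- Section 4.3.1 holds or discontinues cisplatin for toxicity.
- Section 10.0 requires weekly toxicity assessment during radiation.
- Section 13.0 removes patients for grade 4 non-hematologic toxicity (with a physician exception) or on safety grounds.
- Sections 4.3.2 and 6.3 refer re-irradiation to departmental tissue limits.
- Section 17.3 requires serious adverse event reports.
- Section 16.3 places phase II trials under a Data and Safety Monitoring Committee, with procedures set at activation under plans not reproduced here.

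A reader might infer that a harmful regimen would certainly run to full accrual unreviewed. The documents do not support that, because the committee or the investigator may act at any time. They support only that it could, since none of these provisions states an aggregate threshold.

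A reader might also multiply each Section 11.4 rate by 54. That overstates the burden: the risks depend on the irradiated site, and no patient has every organ at risk. Nor is the 25-30% myelosuppression figure a severe-toxicity rate.

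**Conclusion.** The point holds in this form. The stated reason for omitting a stopping rule conflicts with the protocol's own toxicity figures. No aggregate trigger is stated, so excess toxicity could accumulate to full accrual without a pre-specified review. The planned comparison by HRR status cannot show whether the regimen is tolerable overall.

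The contradiction needs no assumption beyond the cited 12% carrying over to this population, and any rate well above zero would suffice. The operating characteristics do rest on assumptions: the ceilings, the look schedule and the way the Section 3.3 categories combine. They show that a simple rule has useful sensitivity. They also show that a ceiling below the rate already expected would pause accrual often, at 33-42% for the 15% ceiling if the true rate is 21.5-23.2%. The 8% false-pause figure applies only when the true rate equals the ceiling.

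This is something the sponsor should change. It is not evidence that the regimen is too toxic.

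**What to change.** 1. Reconcile the Section 14.0 sentence with Section 3.3 (Rationale for Concurrent Cisplatin and RT) and Sections 11.1 to 11.4.
2. Pre-specify an aggregate trigger on severe treatment-related toxicity, starting from the Section 11.1 definition, checked at set enrolment counts such as 10, 20, 30 and 40 treated patients. Reaching it pauses accrual for review by the existing Data and Safety Monitoring Committee. The sponsor's clinicians set the event definition and the ceiling, consistent with the rates the protocol already expects. Publish the operating characteristics over a range of true rates, and say how patients still inside the 2-month window are counted.
3. Report overall toxicity rates with exact 95% confidence intervals in all treated patients, in addition to the comparison by HRR status.

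If the sponsor prefers to rely on the committee alone, Section 14.0 should justify that choice and state the committee's review schedule. This is weaker than a numerical trigger but would replace the present premise.

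The cost is protocol wording and a running count, with no increase in sample size. The downsides are a false-pause risk that depends on the ceiling, and roughly 4-5 further patients enrolled before each look is complete.
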